9.2.1.1. Suspected Unexpected Serious Adverse Reactions

Suspected unexpected serious adverse reactions (SUSARs) are serious events that are not listed in the IB and that the investigator identifies as related to investigational product or procedure. United States 21 CFR 312.32 and European Union Clinical Study Directive 2001/20/EC, and European regulation 536/2014 and the associated detailed guidances or national regulatory requirements in participating countries require the reporting of SUSARs. Lilly has procedures that will be followed for the identification, recording, and expedited reporting of SUSARs that are consistent with global regulations and the associated detailed guidances.

The sponsor has a legal responsibility to notify both the local regulatory authority and other regulatory agencies about the safety of a study intervention under clinical investigation. The sponsor will evaluate the reported SAEs, including confirmation of relatedness and assessment of expectedness. The sponsor has processes for safety reports for identification, recording, and expedited reporting of SUSARs according to local regulatory requirements. The sponsor will comply with country-specific regulatory requirements relating to safety reporting to the regulatory authority, Institutional Review Boards (IRB)/Independent Ethics Committees (IEC), and investigators.

9.2.2. Adverse Events of Special Interest

Adverse events of special interest will include the following:

- Infections (including TB, herpes zoster, or opportunistic infections)
- Malignancies
- Hepatic events (see Section 9.4.5)
- Major adverse cardiovascular events (MACE) (see Section 9.4.7)
- Venous thromboembolism (DVT and PE)
- Arterial thromboembolic events (ATE)

Investigators will provide details on these AEs as instructed on the eCRF and may be asked for additional description by Lilly.

9.2.3. Complaint Handling

Lilly collects product complaints on investigational products and drug delivery systems used in clinical studies in order to ensure the safety of study participants, monitor quality, and facilitate process and product improvements.

Patients (or parents/legal guardians) will be instructed to contact the investigator as soon as possible if they have a complaint or problem with the investigational product so that the situation can be assessed.

9.3. Treatment of Overdose

Baricitinib single doses up to 40-mg and multiple doses of up to 20-mg daily for 10 days have been administered in clinical studies without dose-limiting toxicity. Pharmacokinetic data of a single dose of 40-mg in healthy volunteers indicate that >90% of the administered dose is

expected to be eliminated within 24 hours. In case of an overdose, the patient should be monitored for signs and symptoms of adverse reactions. Patients who develop adverse reactions should receive appropriate treatment.

9.4. Safety

Any clinically significant findings from electrocardiogram (ECG) testing, physical examination, vital signs measurements, or laboratory measurements that result in a diagnosis and that occur after the patient receives the first dose of investigational product should be reported to Lilly or its designee as an AE via eCRF.

9.4.1. *Electrocardiograms*

A single 12-lead standard ECG will be obtained locally at screening and read by a physician qualified to read pediatric ECGs (the investigator or qualified designee) at the site to determine whether the patient meets entry criteria. Electrocardiograms may be obtained at additional times when deemed clinically necessary.

9.4.2. *Vital Signs*

For each patient, vital signs measurements should be conducted according to the Schedule of Activities (Section 2).

Any clinically significant findings from vital signs measurement that result in a diagnosis and that occur after the patient receives the first dose of study treatment should be reported to Lilly or its designee as an AE via electronic data entry.

9.4.3. *Laboratory Tests*

For each patient, laboratory tests detailed in [Appendix 2](#) should be conducted according to the Schedule of Activities (Section 2). Use of local anesthetics (e.g., EMLA cream) consistent with local prescribing information are permitted during the study visit to ease discomfort associated with venipuncture. Owing to blood volume restrictions, some laboratory tests may not be collected. Laboratory samples are recommended to be collected as described in a sponsor-provided weight-based prioritization chart (Appendix 7).

Lilly or its designee will provide the investigator with the results of laboratory tests analyzed by a central vendor, if a central vendor is used for the clinical study.

Any clinically significant findings from laboratory tests that result in a diagnosis and that occur after the patient receives the first dose of investigational product should be reported to Lilly or its designee as an AE via electronic data entry.

9.4.4. *Hepatitis B Virus DNA Monitoring*

Hepatitis B virus DNA testing will be performed in enrolled patients who tested positive for HBcAb at screening (refer to the Schedule of Activities [Section 2]).

Patients who are HBcAb positive and HBV DNA negative (undetectable) at screening will require measurement of HBV DNA as shown in the Schedule of Activities (Section 2) and the follow-up visit, regardless of their hepatitis B surface antibody (HBsAb) status.

The following actions should be taken in response to HBV DNA test results:

- If a single result is obtained with a value “below limit of quantitation,” the test should be repeated within approximately 2 weeks.
- If the repeat test result is “target not detected,” monitoring will resume according to the study schedule.
- If the patient has 2 or more test results with a value “below limit of quantitation,” HBV DNA testing should be performed approximately once per month for the remainder of the study and referral to a hepatologist is recommended.
- If a result is obtained with a value above the limit of quantitation, at any time during the study, the patient will be permanently discontinued from investigational product (see Section 8.1.2) and should be referred to a hepatology specialist.
 - In selected cases, investigators may temporarily continue investigational product in accordance with current immunomodulator management in the setting of HBV DNA positivity. This option may be considered in consultation with Lilly (or its designee) and evaluation of individual patient risks and benefits.

9.4.5. Hepatic Safety Monitoring and Data Collection

If a study patient experiences elevated ALT ≥ 3 x ULN, ALP ≥ 2 x ULN, or elevated TBL ≥ 2 x ULN, liver testing (Appendix 4) should be repeated within 3 to 5 days including ALT, AST, ALP, TBL, direct bilirubin, gamma-glutamyl transferase, and creatine phosphokinase to confirm the abnormality and to determine if it is increasing or decreasing. If the abnormality persists or worsens, clinical and laboratory monitoring should be initiated by the investigator and in consultation with the study medical monitor. Monitoring of ALT, AST, TBL, and ALP should continue until levels normalize or return to approximate baseline levels. Discontinuation criteria of investigational products, either temporary interruption or permanent discontinuation, due to abnormal ALT, AST, TBL, or ALP, are detailed in Section 8.1.

Additional safety data should be collected via the hepatic eCRF if 1 or more of the following conditions occur:

- ALT ≥ 5 x ULN confirmed by repeat testing
- ALP ≥ 2 x ULN confirmed by repeat testing
- TBL ≥ 2 x ULN confirmed by repeat testing (except for cases of known Gilbert’s syndrome)
- Permanent discontinuation of investigational product due to hepatic event or hepatic laboratory abnormality
- Hepatic SAE

Refer to [Appendix 4](#) for a description of hepatic laboratory values that warrant exclusion from the study, temporary or permanent discontinuation of investigational product (Section 8.1), or additional safety collection via the hepatic eCRF.

9.4.6. Safety Monitoring

Lilly will periodically review evolving aggregate safety data within the study by appropriate methods.

If safety issues are identified, the Data Monitoring Committee (DMC) (refer to Interim Analyses section, Section 10.3.7) can request additional analyses of the safety data or request changes to the conduct of the study.

The Lilly clinical research physician/scientist will monitor safety data throughout the course of the study. Lilly will review SAEs within time frames mandated by company procedures. The Lilly clinical research physician will, as is appropriate, consult with the functionally independent Global Patient Safety therapeutic area physician or clinical scientist and periodically review trends in safety data and laboratory analytes. Any concerning trends in frequency or severity noted by an investigator and/or Lilly (or designee) may require further evaluation.

All deaths and SAE reports will be reviewed by Lilly during the clinical study. These reports will be reviewed to ensure completeness and accuracy. If a death or a clinical AE is deemed serious, unexpected, and possibly related to investigational product, Lilly Global Patient Safety will report the event for regulatory reporting and safety monitoring purposes.

Investigators will monitor vital signs and review findings that may be associated with cardiovascular and venous thrombotic events. Adverse event reports and vital signs will be collected at each study visit. The cardiovascular monitoring plan includes the following:

- Regular monitoring of lipid levels
- Potential MACE (cardiovascular death, myocardial infarction [MI], stroke), other cardiovascular events (such as hospitalization for unstable angina, hospitalization for heart failure, serious arrhythmia, resuscitated sudden death, cardiogenic shock, coronary interventions), ATE, venous thrombotic events, and noncardiovascular deaths will be identified by the investigative site or through medical review and will be sent to a blinded Clinical Event Committee for adjudication at regular intervals.

9.4.6.1. Venous Thromboembolic Event Assessment

If a patient develops the clinical features of a DVT or PE, appropriate local laboratory tests and imaging is recommended, as necessary, for diagnosis of the event. For confirmed cases, additional laboratory testing should be performed as outlined in [Appendix 5](#). All suspected VTE events will be independently adjudicated by a blinded Clinical Event Committee.

9.4.6.2. Growth Monitoring

Height and weight will be measured at screening and baseline and postbaseline for the assessment of physical growth according to the Schedule of Activities (Section 2). Height, weight, occipital frontal circumference, and growth velocity changes in pediatric patients (both at

an individual and group level) will be reviewed by the DMC. Height measurements will be made using a stadiometer.

Insulin-like growth factor (IGF)-1, the principal mediator of growth hormone, and IGF-binding protein-3, the principal carrier protein for IGF-1, will be collected for the assessment of growth-related disorders. Gonadal hormone (estradiol for females or testosterone for males) will be collected for the assessment of pubertal development with patients 8 to <18 years of age. For each patient, laboratory tests detailed in [Appendix 2](#) should be conducted according to the Schedule of Activities (Section 2).

A semiannual wrist, hand, finger, and anteroposterior (AP) knee radiographs to monitor bone age and long-bone growth is required, with an option to consent to this procedure for patients already enrolled in the study.

If a local addendum is in place that specifies another mode of imaging (e.g., magnetic resonance imaging [MRI] instead of x-ray), the local addendum should be followed. Otherwise, the current protocol amendment should be followed.

Any symptomatic areas of bones/joints will be assessed and investigated as appropriate by study investigators. Any diagnoses made based on symptomatic areas of bones/joints or imaging data will be reported as appropriate (e.g. recorded on eCRF).

For study sites in Germany:

- MRI of the knee will be collected to monitor bone and cartilage growth and/or maturation.
 - MRI of the knee will be collected approximately every 6 months as shown in Section 2 . A central vendor will be used for reading of the MRI images.
 - An x-ray of the knee (anteroposterior) may be collected in place of the MRI in cases where MRI is not possible (e.g., site does not have MRI access, sedation is required, MRI is not medically advisable in the opinion of the investigator, parents/patients do not consent). The clinical site will document the rationale for collecting x-rays vs. MRIs. An appropriate physician at the clinical site will read the x-ray image, and if it is determined that the patient does not have growth potential (that is, the patient has completed skeletal maturity), then no further knee x-rays will be required. The clinical sites will document the decision that a patient has reached skeletal maturity.
- External tibial length measurement will be collected as an additional assessment of growth.
 - External tibial length will be measured approximately every 3 months as shown in Section 2. Guidance on measuring external tibial length will be provided by the Sponsor.

9.4.6.3. Tanner Stage Scale

The Tanner Stage Scales are a series of line drawings that are designed to assess sexual maturity of the patient, and will be included as a baseline assessment. The line drawings are intended for patient self-assessment; however, this assessment may be also conducted by an appropriate health care professional if the patient and legal guardian agree (Marshall and Tanner 1969, 1970; Tanner and Davis 1985; Chavarro et al. 2017). Assessment by the health care professional will not be completed if the patient and parent do not provide appropriate consent and assent. The self-assessment will only be collected if the appropriate translation of the scale is available for use at the time of the baseline assessment.

9.4.7. Vision-Related Safety Monitoring

9.4.7.1. Fundoscopy

Fundoscopy will be used to assess disc swelling, macular edema, and other structural changes in macular (epiretinal membrane) and optic nerve (optic disc swelling and glaucomatous neuropathy) and retina (neovascularization and retinal detachment). Fundoscopy will be assessed at all visits in each affected eye.

9.4.7.2. Optical Coherence Tomography

Optical coherence tomography (at least stratus II) will be used to assess macular edema and central macular thickness in each affected eye.

9.4.7.3. Cataract Scoring

The Lens Opacities Classification Score (LOCS) II grading will be used for cataract scoring (Chylack et al. 1989). The LOCS II standards for grading cataracts are shown in [Appendix 6](#).

9.4.7.4. Intraocular Pressure

Intraocular pressure will be measured in each affected eye by I-Care, Goldmann tonometry or Tono-Pen, as deemed appropriate.

9.4.7.5. Other Structural or Vision-Related Complications

The following structural changes and vision related complications will be assessed and monitored:

- Band keratopathy
- Synechiae
- Iris bombe
- Glaucoma
- Neovascularization
- Cataract
- Cystoid macular edema
- Optic neuropathy
- Ocular hypertension: >21 mm Hg
- Ocular hypotony: <6 mm Hg
- Glaucomatous field loss and/or glaucomatous optic atrophy
- Epiretinal membrane formation, and
- Visual deterioration: worsening by 0.3 LogMAR in any eye

9.5. Pharmacokinetics

Not applicable.

9.6. Pharmacodynamics

Refer to Section [10.3.5](#).

9.6.1. Pharmacogenetics

9.6.1.1. Whole Blood Sample for Pharmacogenetic Research

A whole blood sample will be collected for pharmacogenetic analysis as specified in the Schedule of Activities (Section [2](#)) where local regulations allow.

There is growing evidence that genetic variation may impact a patient's response to therapy. Variable response to therapy may be due to genetic determinants that impact drug absorption, distribution, metabolism, and excretion, the mechanism of action of the drug, the disease etiology, and/or the molecular subtype of the disease being treated. In the event of an unexpected AE, the samples may be genotyped and analysis may be performed to evaluate a genetic association with response to baricitinib. These investigations may be limited to targeted exome sequencing approach of known targets involved in drug metabolism or, if appropriate, genome-wide association studies may be performed to identify regions of the genome associated with the variability observed in drug response. Samples will be used only for investigations related to disease and drug or class of drugs under study in the context of this clinical program.

9.7. Biomarkers

Biomarker research is performed to address questions of relevance to drug disposition, target engagement, pharmacodynamics (PD), mechanism of action, variability of patient response (including safety), and clinical outcome. Sample collection is incorporated into clinical studies to enable examination of these questions through measurement of biomolecules including DNA, RNA, proteins, lipids, and other cellular elements.

Blood for nonpharmacogenetic biomarker research will be collected at the times specified in the Schedule of Activities (Section [2](#)) where local regulations allow.

Samples will be used for research on the drug target, disease process, variable response to baricitinib, pathways associated with JIA or JIA-U, mechanism of action of baricitinib, and/or research method, or in validating diagnostic tools or assay(s) related to JIA or JIA-U.

All samples will be coded with the patient number. These samples and any data generated can be linked back to the patient only by the investigator or site personnel.

Samples will be retained at a facility selected by the sponsor for a maximum of 15 years after the last patient visit for the study, or for a shorter period if local regulations require and ethical review boards impose shorter time limits. The duration allows the sponsor to respond to future regulatory requests related to the investigational product. Any samples remaining after 15 years will be destroyed.

9.8. Medical Resource Utilization and Health Economics

There will be no collection of healthcare resource utilization or calculation of utilities for economic modeling in this study.

10. Statistical Considerations

10.1. Sample Size Determination

The original sample size was determined by the following:

At least 20 and up to 40 patients will be enrolled.

- Baricitinib arm: At least 10 and up to 30 patients (MTX-IR and bDMARD-IR) ; at least 10 MTX-IR patients
- Adalimumab arm: At least 10 MTX-IR patients.

At least 20 MTX-IR (but not bDMARD-IR) patients will be randomized to baricitinib and adalimumab in a 1:1 ratio.

With a total sample size of 30 in the baricitinib arm, and assuming an observed response rate of 66.7%, the study will be able to detect a true baricitinib treatment response rate of greater than 57% with greater than 80% probability. The observed response rate of 66.7% is based on the assumption that 20 out of 30 patients in the baricitinib arm will achieve the primary endpoint. The response rate threshold of 57% was chosen to match the response rate observed for patients with JIA-associated uveitis treated with adalimumab in the SYCAMORE study (Ramanan et al. 2017).

Since the original sample size was determined, the study enrollment has been updated to the following:

- Baricitinib arm: At least 20 patients (MTX-IR and/or bDMARD-IR) evaluable for the primary endpoint.
- Adalimumab arm: At least 4 patients evaluable for the primary endpoint.

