
 To evaluate the safety of baricitinib in children with JIA-U or ANA-positive uveitis 	
 Adverse events including serious adverse events. Permanent discontinuation of investigational product due to AE. Temporary interruption of investigational product.

Abbreviations: AE = adverse event; LogMAR = logarithm of the minimum angle of resolution;

PediACR = Pediatric American College of Rheumatology; SUN = Standardization of Uveitis Nomenclature.

a Response is defined according to the SUN criteria as a 2-step decrease in the level of inflammation (anterior chamber cells) or decrease to 0 through Week 24 in the eye most severely affected at baseline.

Summary of Study Design

Study I4V-MC-JAHW (JAHW) is a multicenter, open-label, active-controlled Phase 3 study in patients with active JIA-U or chronic ANA-positive uveitis without systemic features despite prior treatment with adequate doses of topical steroid therapy and MTX.

Treatment Arms and Duration

The study consists of 2 arms. Patients in the baricitinib arm will receive oral baricitinib at least QD at a fixed dose by age group. Patients in the adalimumab (active control) arm will receive adalimumab as a subcutaneous injection every 2 weeks. The dose will be based on body weight (adalimumab Summary of Product Characteristics [SmPC]).

Study JAHW will be conducted in 2 parts:

- Treatment Period Part A: 24 weeks
- Treatment Period Part B: 260 weeks.

Patients who complete Part A may be eligible to continue to Part B, the open-label extension (OLE) period of the study. Patients on adalimumab will be discontinued after Week 24. Patients who do not continue in the OLE will have a follow-up visit (Visit 801) approximately 28 days after the last dose of the investigational product.

Study Population

This study includes patients from 2 years to less than 18 years old with active JIA-U or chronic ANA-positive uveitis without systemic features despite prior treatment with adequate doses of topical steroid therapy and MTX.

Number of Patients

- Baricitinib arm: At least 20 patients (MTX-IR and/or bDMARD-IR) evaluable for primary endpoint.
- Adalimumab arm: At least 4 patients evaluable for the primary endpoint.

Statistical Analysis

A Bayesian analysis will determine if the study should be considered a positive study or a negative study. The study will be considered positive if the posterior probability is at least 80%

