10.2. Populations for Analyses

Unless otherwise specified, the efficacy and health outcome analyses will be conducted on the modified intent-to-treat (mITT) analysis set in Part A. The mITT set is defined as the patients who take at least 1 age-based dose of investigational product in Part A. Patients will be analyzed according to the treatment to which they were assigned. For the efficacy and health outcomes analysis in Part B, the analysis will be conducted on as-observed data, which is defined in Section 10.3.1. Significant protocol violations will be described in the SAP.

Safety analyses will be carried out on all randomized patients who receive at least 1 dose of investigational product and who did not discontinue from the study for the reason “Lost to Follow-up” at the first postbaseline visit.

Further details of other populations will be described in the SAP.

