10.3. Statistical Analyses

10.3.1. General Statistical Considerations

Statistical analysis of this study will be the responsibility of Lilly or its designee. A detailed SAP describing the statistical methodologies will be developed by Lilly or its designee.

Bayesian analysis will be used as the primary analysis method for the primary endpoint and interim analysis. The posterior probability will be reported and the conclusion will be made based on the prespecified success criteria. The primary endpoint is the proportion of patients with response at Week 24. Response is defined as a 2-step decrease in the level of inflammation (anterior chamber cells) or decrease to zero in the eye most severely affected at baseline, measured by SUN criteria (Jabs et al. 2005). If the study is not stopped for futility, the posterior probability of the treatment response rate exceeding 57% will be calculated, and the study objective will be successfully met (i.e., a positive study) if this probability is at least 80%. The detail of the analyses will be described in the SAP.

Unless otherwise specified, for the endpoints that may relate to both eyes, such as patients with uveitis affecting both eyes, the summary of the data for a given endpoint measure will be based on both affected eyes. The summary statistics may be grouped into “less severely affected eye” and “more severely affected eye,” or “right eye” and “left eye” subgroups. The details will be documented in the SAP.

Efficacy and health outcome endpoints will also be summarized using descriptive statistics for the baricitinib arm and adalimumab arm. No treatment comparison will be conducted.

Continuous data will be summarized in terms of the mean, standard deviation, minimum, maximum, and median. Categorical data will be summarized as frequency counts and percentages.

All safety data will be descriptively summarized.

Any change to the data analysis methods described in the protocol will require an amendment ONLY if it changes a principal feature of the protocol. Any other change to the data analysis methods described in the protocol, and the justification for making the change, will be described in the clinical study report. Additional exploratory analyses of the data will be conducted as deemed appropriate. Complete details of the planned analyses will be documented in the SAP.

The SAP will be approved before the first patient visit in Study JAHW.

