5.2. Determination of Sample Size

The original sample size was determined by the following:

At least 20 and up to 40 patients will be enrolled:

- **Baricitinib arm:** at least 10 and up to 30 patients (MTX-inadequate response [IR] and biologic disease-modifying antirheumatic [bDMARD]-IR); at least 10 MTX-IR patients.
- **Adalimumab arm:** at least 10 MTX-IR patients.

At least 20 MTX- IR (but not bDMARD-IR) patients will be randomized to baricitinib and adalimumab in a 1:1 ratio.

With a total sample size of 30 in the baricitinib arm, and assuming an observed response rate of **CCI**, Study JAHW will be able to detect a true baricitinib treatment response rate of **>CCI** with **>CCI** probability. The observed response rate of **CCI** is based on the assumption that 20 out of 30 patients in the baricitinib arm will achieve the primary endpoint. **CCI**

[REDACTED]

Since the original sample size was determined, Study JAHW enrollment has been updated to the following:

Baricitinib arm: at least 20 patients (MTX-IR and/or bDMARD-IR) evaluable for the primary endpoint.

Adalimumab arm: at least 4 patients evaluable for the primary endpoint.

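### Protocol 10.1 presents a posterior probability at an assumed result as the chance of detecting a true response rate above 57%

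*Protocol*

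**What the plan says.** Protocol 10.1 takes 30 baricitinib patients and an assumed observed response rate of 66.7%, and concludes that "the study will be able to detect a true baricitinib treatment response rate of greater than 57% with greater than 80% probability". It explains the 66.7%: "The observed response rate of 66.7% is based on the assumption that 20 out of 30 patients in the baricitinib arm" reach the primary endpoint. It then adds: "Since the original sample size was determined, the study enrollment has been updated to the following", and lists at least 20 evaluable patients on baricitinib and at least 4 on adalimumab. No probability is attached to the updated numbers.

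The success rule is given elsewhere. In the Synopsis: "The study will be considered positive if the posterior probability is at least 80"% that the baricitinib response exceeds 57%. Protocol 10.3.1 applies the same rule to Pr(θ > 57%): "the study objective will be successfully met (i.e., a positive study) if this probability is at least 80"%. Protocol 10.3.3.1 supplies the Beta(1,1) prior and a final stage of up to 30 patients.

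SAP 5.2 repeats the sample-size sentence ("With a total sample size of 30 in the baricitinib arm, and assuming an observed response rate of" and so on), but its figures are redacted in the public copy.

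**The concern.** In a sample-size section, being able to detect a true rate with a stated probability means the chance that the design succeeds when the drug has that rate. The 80% in Protocol 10.1 is tied to an assumed observed result instead. Once 20/30 has been observed, nothing is left to detect: the outcome is settled by the rule.

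An ethics committee or assessor could take from 10.1 that a drug with a true rate above 57% has better than an 80% chance of a positive study. That would colour the judgement of whether the enrolment is adequate, and the reading of a negative result. The sentence is also the only quantitative sample-size justification in the current Protocol, so the 80% is easily carried over to the updated minimum of 20, for which nothing is stated.

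**Working it through.** **Inputs.** Threshold 57% and posterior cut-off 80% (Protocol 10.3.1); prior Beta(1,1) (10.3.3.1); n = 30 with 20 observed responders, and the updated minimum of 20 (10.1); futility stops at 2 or fewer of 10 and 6 or fewer of 20 (10.3.7). The Protocol gives no true planning rate, so the true rates below are scenarios.

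**Step 1: reproduce the stated figure.** With y responders among n, the posterior is Beta(1 + y, 1 + n − y).

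- n = 30, y = 20: Beta(21, 11), Pr(θ > 0.57) = 0.848
- n = 30, y = 19: Beta(20, 12), Pr(θ > 0.57) = 0.745

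So the stated figure of more than 80% is the posterior at 20/30, and 20 is the smallest passing count. A Jeffreys prior gives 0.858 and 0.756, hence the same cut-off.

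**Step 2: the cut-off at n = 20.**

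- y = 14: Beta(15, 7), 0.868
- y = 13: Beta(14, 8), 0.748

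Fourteen responders are needed. A posterior of at least 80% holds at the passing boundary of any sample size, so it cannot by itself justify 30.

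**Step 3: chance of a positive study at a fixed true rate p.** P(positive) = P(Bin(n, p) ≥ c), with c = 20 for n = 30 and c = 14 for n = 20.

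| True rate p | n = 30 | n = 20 |
|---|---|---|
| 57% | 18.9% | 17.2% |
| 60% | 29.1% | 25.0% |
| 66.7% | 58.5% | 47.9% |
| 70% | 73.0% | 60.8% |
| 75% | 89.4% | 78.6% |

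Solving for P(positive) = 80% gives p = 71.8% (n = 30) and 75.5% (n = 20).

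**Step 4: futility stops.** A patient series stopped at 6/20 could reach at most 6 + 10 = 16 of 30, below 20, so the second look removes no success. A series stopped at 2/10 could reach at most 2 + 10 = 12 of 20, below 14, so at n = 20 nothing changes. At n = 30 it could reach 2 + 20 = 22, so there is a small loss: the exact calculation gives 18.87, 58.47 and 89.42% at true rates of 57, 66.7 and 75%, against 18.88, 58.48 and 89.43% without stops.

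**Step 5: sizes between 20 and 30.** The cut-off moves in whole patients, so the chance does not rise steadily with n. At a true 66.7% it runs from 41.9% (n = 21, 15 needed) to 63.6% (n = 29, 19 needed). The true rate needed for an 80% chance runs from 70.8% (n = 29) to 76.7% (n = 21). The figures at 20 and 30 are therefore not bounds.

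**Step 6: averaging over the prior.** With θ uniform on (0.57, 1), the mean of P(positive) is 80.3% at n = 30 and 75.1% at n = 20.

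**The case against.** The arithmetic in 10.1 is right and its condition is disclosed: power would not be computed from an observed rate, so a careful reader can see that a posterior is meant, and the Synopsis and 10.3.1 word the rule correctly. That stands. It limits the fault to wording, but the words still state a property that the design does not have.

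The stronger point is Step 6. Averaged over the Protocol's own prior above 57%, the chance of success at n = 30 is 80.3%, so even the feared misreading is about right on average. But the sentence does not average over a prior; it conditions on 20/30. The same average at the updated minimum is 75.1%. Nor can any design have an 80% chance at every rate just above its own threshold, which is a reason to say at which rates it does.

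It can also be said that the sentence describes the original enrolment and makes no claim for 20 patients. That is true, and the missing figure for n = 20 is an omission rather than a misstatement. The sentence nevertheless remains in force with nothing beside it.

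Finally, redacted parts of the SAP may hold operating characteristics. The absence is therefore shown for the Protocol only.

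**Conclusion.** The concern holds. The probability above 80% in Protocol 10.1 is the posterior at the smallest passing result (0.848 at 20/30), not the chance that the study is positive. At a fixed true rate that chance reaches 80% only from about 71.8% with 30 patients or 75.5% with 20. If the true rate equalled the 66.7% that 10.1 assumes as observed, the chance would be 58.5% or 47.9%.

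This rests on the stated prior, threshold and cut-off, on independent binary outcomes with a common response rate, and on true rates chosen here for illustration. Responder status is taken as final after handling of missing data. The decision rule, the futility limits and the patient numbers are not in question. It should be fixed, because a sample-size section ought to state correctly what the design can do.

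**What to change.** In Protocol 10.1, replace the sentence with text such as:

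> With 30 baricitinib patients, an observed 20/30 (66.7%) gives a posterior probability of 0.848 that the true response rate exceeds 57%; 20 is the smallest number of responders that meets the success criterion. At true response rates of 57%, 66.7% and 75%, the probability of a positive study is 18.9%, 58.5% and 89.4%. If 20 patients are analysed (the updated minimum), 14 responders are needed and these probabilities are 17.2%, 47.9% and 78.6%.

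Tie the 14 responders to an analysed N of 20, not to 20 evaluable patients: under Protocol 10.2, "The mITT set is defined as the patients who take at least 1 age-based dose of investigational product in Part A", and that number may exceed the evaluable count. A short table for n = 20 to 30 is optional but would show the uneven steps between those sizes. The 20 of 30 is reported here only as what the rule implies at N = 30; it does not reinstate a fixed cut-off for other sizes. Bring SAP 5.2 into line.

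The cost is text only. No rule, limit or patient number changes; the stated figure becomes less favourable.
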